#### 12.2.2.2 Progression free survival

The primary analysis of the co-primary endpoint, PFS, will occur when it is expected that 458 PFS events have occurred (65% maturity). PFS based upon the BICR data will be analysed using a stratified log-rank test adjusting for the same factors as for OS. The effect of treatment will be estimated by the HR together with its corresponding 97.5% CI and p-value for the full ITT population. Kaplan-Meier plots of PFS will be presented by treatment arm. Summaries of the number and percentage of patients experiencing a PFS event, and the type of event (RECIST 1.1 or death) will be provided along with median PFS for each treatment.

The assumption of proportionality will be assessed in the same way as for OS. The analysis will be based on the programmatically derived PFS using BICR data.

Sensitivity analyses will be performed to assess possible evaluation-time bias that may be introduced if scans are not performed at the protocol-scheduled timepoints. The midpoint between the time of progression and the previous evaluable RECIST assessment will be analysed using a log-rank test. For patients whose death was treated as PFS event, the date of

death will be used to derive the PFS time used in the analysis. This approach has been shown to be robust to even highly asymmetric assessment schedules (Sun and Chen 2010).

Attrition bias will be assessed by repeating the PFS analysis except that the actual PFS event times, rather than the censored times, of patients who progressed or died in the absence of progression immediately following 2, or more, non-evaluable tumour assessments will be included. In addition, patients who take subsequent therapy prior to progression or death will be censored at their last evaluable assessment prior to taking the subsequent therapy. This analysis will be supported by a Kaplan-Meier plot of the time to censoring where the censoring indicator of the PFS analysis is reversed.

Ascertainment bias will be assessed by analysing site Investigator data. The stratified log-rank test will be repeated on the programmatically derived PFS using the site Investigator data based upon RECIST. The HR and CI will be presented.

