1.3 Number of Subjects

The sample size for this study was selected to be consistent with the research hypothesis as described in Section 1.2 of the CSP.

The two co-primary endpoints of this study are OS and PFS. To control for type-I error, a significance level of 2.5% will be used for analysis of OS and a significance level of 2.5% will be used for analysis of PFS. The study will be considered positive (a success) if either the PFS analysis results and/or the OS analysis results are statistically significant.

Approximately 702 patients will be randomised 2:1 to obtain 491 death events in the ITT population (70% maturity). The primary PFS analysis DCO will occur when it is expected that 458 PFS events have occurred (65% maturity). If the true PFS HR is 0.67, the study will provide at least 95% power to demonstrate a statistically significant difference for PFS with a 2-sided significance level of 2.5% in the ITT population; this translates to a 5-month benefit in median PFS over 10 months on placebo if PFS is exponentially distributed. The smallest treatment difference that would be statistically significant is a HR of 0.8. A recruitment period of approximately 22 months and a follow-up period of 14 months are expected for the PFS endpoint. Therefore it is anticipated that this PFS analysis could be performed approximately 36 months after the first patient has been randomised.

The primary OS analysis DCO will occur when it is expected that 491 OS events have occurred (70% maturity). If the true OS HR is 0.73, this number of death events will provide at least 85% power to demonstrate a statistically significant difference for OS, assuming a 2.5% 2-sided significance level in the ITT population; this translates to an 8-month benefit in median OS over 22 months on placebo if OS is exponentially distributed (Butts et al 2014). The smallest treatment difference that would be statistically significant is a HR of 0.81. A recruitment period of approximately 22 months and a follow-up period of 40 months are expected for the OS endpoint. Therefore it is anticipated that this OS analysis could be performed at approximately 62 months after the first patient has been randomised.

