Additionally, summary statistics for the number of weeks between the time of progression and the last RECIST assessment prior to progression will be presented for each treatment group.

Summaries of the number and percentage of patients who miss two or more consecutive RECIST assessments will be presented for each treatment group.

All of the collected RECIST 1.1 data will be listed for all randomised patients. In addition, a summary of new lesions (i.e., sites of new lesions) will be produced.

Sensitivity Analyses

The following sensitivity analyses will be performed:

- Evaluation-Time bias

Sensitivity analyses will be performed to assess possible evaluation-time bias that may be introduced if scans are not performed at the protocol-scheduled timepoints. The midpoint between the time of progression and the previous RECIST assessment will be analysed using a stratified log-rank test, as described for the co-primary analysis of PFS. For patients whose death was treated as PFS event, the date of death will be used to derive the PFS time used in the analysis. This approach has been shown to be robust to even highly asymmetric assessment schedules ([Sun and Chen 2010](#)). To support this analysis, the mean of subject-level average inter-assessment times will be tabulated for each treatment. This approach will use the BICR data.

- Attrition bias

Attrition bias will be assessed by repeating the co-primary PFS analysis except that the actual PFS event times, rather than the censored times, of patients who progressed or died in the absence of progression immediately following two, or more, tumour assessments will be included. In addition, patients who take subsequent therapy prior to their last evaluable RECIST assessment or progression or death will be censored at their last assessment prior to taking the subsequent therapy. This analysis will be supported by a Kaplan-Meier plot of the time to censoring where the censoring indicator of the PFS analysis is reversed. This approach will use the BICR data.

- Ascertainment bias

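### The single attrition-bias analysis of PFS makes two opposing censoring changes at once, so under some patterns it can hide bias from the missed-visit rule; the two changes should be reported separately

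*SAP*

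**What the plan says.** SAP section 3.2.1.2 fixes two features of primary PFS. A progression or death after two or more missed visits is not counted; the patient is censored at the last assessment before the gap. Subsequent anti-cancer therapy is ignored, so events after it count.

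The attrition-bias paragraph of SAP section 4.2.1.2 changes both in one analysis:

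- **Change A.** Actual event times replace censored times, so that "patients who progressed or died in the absence of progression immediately following two, or more, tumour assessments will be included".
- **Change B.** It then adds that "patients who take subsequent therapy prior to their last evaluable RECIST assessment or progression or death will be censored at their last assessment" before the new therapy.

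Protocol section 12.2.2.2 has the same combination; its second part reads "patients who take subsequent therapy prior to progression or death will be censored at their last evaluable assessment" before that therapy. SAP Table 8 and protocol Table 15 each list one attrition-bias item for PFS. SAP section 4.2.1.2 also plans a forest plot setting the sensitivity HRs beside the primary HR.

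The wording of A differs between the documents. The protocol refers to two or more *non-evaluable* assessments; the SAP has no qualifier, so read literally it refers to two or more assessments of any kind.

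**The concern.** A sensitivity analysis should show which departure from the primary rule matters. Here A turns censored observations into events and B turns events into earlier censoring, and one HR comes out. If that HR agrees with the primary HR, the reader cannot tell whether neither change mattered or whether two shifts offset each other.

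The substantive question is whether the missed-visit rule distorts the PFS comparison. A alone answers it. Adding B to the same run mixes in a different question, namely what PFS would look like if follow-up stopped at new therapy. B can also introduce informative censoring of its own, because patients who switch early are unlikely to have the same outlook as those who do not.

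New therapy before progression is foreseeable. Protocol section 3.2.3.4 expects other PD-1/PD-L1 agents to become available during the study, and section 6.3 keeps patients who start other therapy under tumour assessment until confirmed progression.

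**Working it through.** **1. The plan's own PFS figure.** SAP section 1.3 gives "Approximately 702 patients will be randomised 2:1", "458 PFS events have occurred (65% maturity"), "a significance level of 2.5% will be used for analysis of PFS" and "If the true PFS HR is 0.67, the study will provide at least 95% power".

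- Information for log HR: 458 × (2/3) × (1/3) = 101.8; square root 10.088.
- Power: Φ(0.4005 × 10.088 − 2.241) = Φ(1.799) = 96.4%, where 0.4005 = −ln 0.67. The stated figure of at least 95% is reproduced.
- Smallest significant HR: exp(−2.241/10.088) = 0.801, against the stated 0.8.
- At the final level of 2.19%, power is 96.0% and the smallest significant HR 0.797.

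The point below does not touch these figures.

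**2. How each rule treats the affected patients.**

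| Patient | Primary | A alone | B alone | A+B as planned |
|---|---|---|---|---|
| Event after two or more missed visits, no new therapy | censored | event | censored | event |
| Event after new therapy, no gap | event | event | censored | censored |
| New therapy, then event after a gap | censored | event | censored | not specified |

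On event counts, A and B always oppose each other. Their effect on the HR depends on which arm the patients are in.

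**3. Size, by simulation.** From the documents: 2:1 allocation, exponential PFS, placebo median 10 months, HR 0.67, 22 months of accrual, data cut-off at 36 months, scans every 8 weeks to week 48 and every 12 weeks after that. Assumptions: the rates of gaps and of new therapy, new therapy starting 0 to 6 months before the event, uniform accrual, exact event times, no strata, and no patient under both rules. The run used 702 × 600 patients and an unstratified Cox model; events are scaled to 702 patients. Rates are MEDI4736/placebo.

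| Gap rate | Therapy rate | Primary HR | A alone | B alone | A+B | Events: primary, A, B, A+B |
|---|---|---|---|---|---|---|
| 10%/4% | 10%/4% | 0.637 | 0.673 | 0.600 | 0.640 | 464, 503, 429, 468 |
| 20%/5% | 20%/5% | 0.583 | 0.673 | 0.499 | 0.602 | 431, 503, 371, 444 |
| 4%/10% | 4%/10% | 0.702 | 0.673 | 0.735 | 0.699 | 472, 503, 443, 475 |
| 10%/10% | 10%/10% | 0.667 | 0.673 | 0.661 | 0.667 | 453, 503, 408, 458 |
| 10%/4% | 4%/10% | 0.637 | 0.673 | 0.666 | 0.704 | 464, 503, 435, 474 |
| 10%/4% | 5%/5% | 0.637 | 0.673 | 0.634 | 0.672 | 464, 503, 441, 480 |

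Reading the rows:

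- First row: A moves the HR by 0.673 − 0.637 = +0.036 and B by 0.600 − 0.637 = −0.037; together they move it by +0.003.
- Second row: shifts of +0.090 and −0.084 leave +0.019.
- Third row, both imbalances towards placebo: −0.029 and +0.033 leave −0.003.
- Fourth row, equal rates: each change moves the HR by 0.006 at most.
- Fifth row, opposite imbalances: +0.036 and +0.029 become +0.067.
- Sixth row, balanced new therapy: the combination shows nearly all of A's shift (+0.035 of +0.036).

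In every row A alone returns 0.673, the HR with no missed visits, so the gap between A and the primary is the bias from the missed-visit rule. B's shift comes from B's own censoring.

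Uniform accrual gives 503 events at month 36 without missed visits, more than the planned 458. A separate run with accrual proportional to t², which matches the stated event calendar, showed the same pattern: with gaps 4%/12% and new therapy 6%/15%, the primary HR was 0.727, A 0.681, B 0.791 and the combination 0.728.

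**The case against.** **Cancellation is a special case.** This stands. A reader might infer that the two changes always push the HR in opposite directions. They do so only when both rates are unbalanced towards the same arm. Nothing in the documents says that missed visits and early switching go together; toxicity could cause missed visits in one arm while progression drives switching in the other.

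**Two biases do not cancel here.** This also stands. A reader might take the combined HR to hide two biases in the primary analysis. SAP section 3.2.1.2 counts events after new therapy by definition, so B corrects nothing in the primary analysis. What can be masked is bias from the missed-visit rule.

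**Other outputs bear on the question.** A reader might call this the only planned check. It is not. By arm, SAP section 4.2.1.2 also plans counts of patients missing two or more consecutive assessments, premature censoring, discontinuation before progression, and time to first subsequent therapy or death; a reversed-censoring Kaplan-Meier plot supports the attrition analysis. These could reveal the imbalance that masking needs. None gives a PFS HR for A or B alone, and time to first subsequent therapy is a different endpoint because new therapy is itself an event.

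**The lost qualifier is a drafting slip.** Largely so. Change A replaces censored times by event times, and under section 3.2.1.2 the patients who have both are essentially those caught by the missed-visit rule. The wording still needs correcting. Copying the protocol's word back would not do: SAP section 6 moved censoring from the last evaluable assessment to the last assessment, so a non-evaluable scan no longer counts as a gap.

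**The analysis is only supportive.** True, and it limits the importance of the point.

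**Conclusion.** The point holds in a limited form. One planned HR combines two opposing changes, and neither document plans either change alone. Under same-direction imbalances of 10% against 4%, a shift of about 0.036 from the missed-visit rule is almost entirely hidden; at 20% against 5%, most of a 0.090 shift is. Under opposite imbalances the combined HR overstates the effect of the missed-visit rule, and under balanced rates little happens. All rates are assumptions, so this shows what can occur and does not predict what did.

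A reader might go further and doubt the co-primary PFS result. The documents do not support that: the primary test, its alpha and its power do not depend on this analysis. What is weakened is a robustness statement resting on agreement between the combined HR and the primary HR.

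**What to change.** In SAP section 4.2.1.2 and Table 8, replace the single item by two named sensitivity analyses, each otherwise identical to the primary analysis:

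1. **Missed-visit rule.** Use actual event times for patients who progressed or died after *two or more missed tumour assessments*, with missed visits defined as in section 3.2.1.2.
2. **Subsequent therapy.** Censor at the last assessment before new therapy, and label the result as a different question from the primary PFS definition. Choose between last assessment and last evaluable assessment, since the present sentence uses both.

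Report each with its HR, confidence interval and number of patients reclassified by arm, on the planned forest plot. The combined analysis may stay as a third row, provided the SAP says which rule takes precedence for a patient who starts new therapy and then has an event after a gap.

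Cost: a wording change, one extra model run and one or two extra forest-plot rows. No new data are needed.

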4.2.2 Secondary efficacy endpoints

4.2.2.1 Proportion of patients alive at 24 months (OS24)

OS24 will be analysed (using the Kaplan-Meier curve) and presented by treatment arm. For each treatment arm, the survival rate at 24 months based on Kaplan-Meier method will be presented, along with its 95% confidence interval. The computation of the confidence interval will be based on a log(-log(.)) transformation.

For the comparison between treatments (sub-study B only), the test will be based on the method described in Klein 2007 (Klein et al 2007). The test statistic and its variance estimate are as follows:

- test statistic = $\ln \frac{\ln \hat{S}_1(t)}{\ln \hat{S}_2(t)}$
- Variance estimate = $\frac{\hat{\sigma}_1(t)^2}{\ln^2 S_1(t)} + \frac{\hat{\sigma}_2(t)^2}{\ln^2 S_2(t)}$

where $\hat{\sigma}_i(t)^2 = \sum_{t_i \leq t} \frac{d_i}{n_i(n_i - d_i)}$ is the variance derived from Greenwood's formula $S(t)$ and can be estimated from standard software packages, where d_i and n_i refer to the number of deaths and patients at risk for each risk set.

The z-statistic is then calculated as:
$$\frac{\text{test statistic}}{\sqrt{\text{variance estimate}}}$$

For stratified analysis, the test statistic and its variance estimate in each strata will be combined by weighting inversely proportionately according to each within stratum variance (Whitehead and Whitehead 1991). A Z-test will be performed and the p-value from the test will be presented.

4.2.2.2 Objective response rate

The ORR will be based on the programmatically derived RECIST outcome using the BICR data. The treatment comparison of ORR will be based on a Fisher's exact test using mid p-values. A binary response variable for ORR will be used for the analysis with the categories of CR and PR vs SD, PD and NE. The results of the analysis will be presented in terms of the proportion of responders and a p-value.

The mid-p-value modification of the Fisher exact test amounts to subtracting half of the probability of the observed table from Fisher's p-value.

$$\text{Fisher's exact test mid p-value} = \text{Two sided p-value} - \frac{\text{Table probability}}{2}$$

This analysis of ORR will be repeated using the results of the programmatically derived outcome using the site investigator data based upon RECIST as a sensitivity analysis to confirm the results of the primary analysis based on the site investigator tumour data. An additional sensitivity analysis will be performed on programmatically derived outcomes using BICR tumour data based upon RECIST modified for confirmation of progression to determine if there is any difference when using progression confirmation rules. Finally, an exploratory analysis of ORR using the irRECIST 1.1 data obtained from the BICR will be performed where the above analysis will be repeated.

Summaries will be produced that present the number and percentage of patients with a tumour response (CR/PR) based upon the number of patients with measurable disease at baseline per BICR or investigator as appropriate (see Section 3.2.2.2). For each treatment arm, best objective response (BoR) will be summarised by n (%) for each category (CR, PR, ND, SD, PD, NE). This will be produced for the BICR of RECIST only. No formal statistical analyses are planned for BoR.

